### **Study duration and dates**

- Estimated enrolment duration: 24 months
- Start of documentation: 01.03.2021
- Estimated follow up: up to 8 documentation points within 36 months
- Last patient In: 01.03.2023
- Last patient Out/End of documentation 01.03.2026
- Database lock planned date: 01.05.2026
- Estimated Report date: 01.01.2027

The starting dates of this NIS will differ in Germany, Austria and Switzerland according to the operational set up.

### 7.3 EVALUATION CRITERIA

Study examinations will take place at months 3, 6, 9, 12, 18, 24 and 36.

Survey of concomitant medication and Cemiplimab treatment will take place at all study examinations.

Tumor Evaluation will be conducted according to guidelines and evaluation according to RECIST v.1.1 (Appendix 16.2). Computed tomography (CT) scan or magnetic resonance imaging (MRI) of chest, abdomen and pelvis and additional tumor bearing areas as well as digital photography of cutaneous lesions are preferred methods.

#### Adverse Events

##### *Evaluation of Severity*

The severity of SAEs will be graded using the Common Terminology Criteria for AE (CTCAE)5.0 as documented in the medical record. Questionnaire: EORTC – QoL Core 30.

The investigator should assess irAE severity based on the nature of the event, intensity of signs and/or symptoms, current functional impairment, and potential long-term health hazards related to the event. The following scale is provided only as general guidance:

- **Mild:** Does not interfere in a significant manner with the patient's normal functioning level. It may be an annoyance. Prescription drugs are not ordinarily needed for relief of symptoms, but may be given because of personality of the patient.
- **Moderate:** Produces some impairment of functioning but is not hazardous to health. It is uncomfortable or an embarrassment. Treatment for symptom may be needed.
- **Severe:** Produces significant impairment of functioning or incapacitation and is a definite hazard to the patient's health. Treatment for symptom may be given and/or patient hospitalized.

##### *Evaluation of Causality*

The investigator should assess the potential relationship between the irAE or SAE and patient's treatments, which could be medications or medical procedures administered for

CSCC or for any other condition. There are 2 alternative (mutually exclusive) options for this assessment. Select the one that appears most likely:

- **Not treatment-related:** The irAE/SAE occurred independently of any of the patient's treatments. An alternative cause is suspected, or otherwise there is no reason to suspect that one or more of the patient's treatments may have caused the irAE/SAE
- **Treatment-related:** The irAE/SAE was likely caused by one or more of patient's treatments

If treatment-related, the suspected treatment(s) should be identified.

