### PARAMETER AND DEFINITIONS for the CRF's

Outcome(s)	Specific parameter	Definition	Record in Visit (month)
Clinical outcomes	Mortality, all cause, advCSCC related, and date of death	Defined as death due to all cause or disease related	-
	OS from diagnosis	Defined as time from 1 st Cemiplimab treatment until death from any cause, censoring for date of most recent follow-up in surviving patients	-
	Progression	Defined as documented in medical records	3,6,9,12,18,24,36
	Date of progression	Defined as date of first documented progression in the medical record	3,6,9,12,18,24,36
	Time to next treatment (TTNT)	Defined as time from start of Cemiplimab treatment to the start of next systemic therapy or death	-
	PFS	Defined as documented start of systemic Cemiplimab therapy until disease progression or death	3,6,9,12,18,24,36
	Patient		male / female

characteristics	Gender		
	Nationality		Baseline
	Year of birth		Baseline
	Skin phototype	Defined as Type 1, 2.....6	Baseline
	Informed consent		Baseline
	Comorbidities	Auto-immune-disease, hematologic disease, severe cognitive impairment, etc.	Baseline and 3,6,9,12,18,24,and 36
	Quality of life data (QoL)	Questionnaire: EORTC – QoL Core 30	Baseline and 3,6,9,12,18,24,and 36
	Pain	Questionnaire: EORTC – QoL Core 30	Baseline and 3,6,9,12,18,24,and 36
	Adverse events (AE) Quality of life data Reasons for discontinuing therapy Frequency of administration	Defined event as yes/no (specify, related/unrelated to anticancer therapy, serious/non-serious as documented in medical records NOTE: We will limit data collection to Common Terminology Criteria for AE (CTCAE)5.0 as documented in the medical record.Questionnaire: EORTC – QoL Core 30  Defined as lack of response, disease progression, toxicities, side effects, therapy completion, patient decision, death, other (specify) Defined as every day (QD), twice a day (BID), every week (QW), every other week (Q2W), every three weeks (Q3W), every four weeks (Q4W), other	Baseline and 3,6,9,12,18,24,and 36
	Adverse events (AE)	Defined event as yes/no (specify, related/unrelated to anticancer therapy, serious/non-serious as documented in medical records NOTE: We will limit data collection to Common Terminology Criteria for AE (CTCAE) 5.0 as documented in the medical record.	Baseline and 3,6,9,12,18, 24,36
Lab results	Lab parameter LDH		Baseline
Status	Date of physical check-up		Status at Baseline

	Organ transplantation		

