### 13.2 SAFETY OBSERVATIONS

- The treating physician should take all appropriate measures to ensure the safety of the patients as per normal practice.
- In case of any AE, the patient must be followed up until clinical recovery is complete and laboratory results have returned to normal, or until progression has been stabilized. This may imply that follow-up will continue after the patient has left the study.
- In case of any AE brought to the attention of the treating physician at any time after cessation of Cemiplimab, and considered by him/her to be caused by Cemiplimab with a reasonable possibility, this should be reported to the *Alcedis GmbH*.

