### 13.3 AE OF SPECIAL INTEREST (AESI)

An AE of special interest (serious or non-serious) is one of scientific and medical concern specific to the product or program, for which ongoing monitoring and rapid communication by the treating physician to *Alcedis GmbH* is required. Such AE normally require thorough documentation and investigation to characterize them.

In the event of an AESI, *Alcedis GmbH* will be informed immediately (i.e., within 24 hours, no later than the following working day) even not fulfilling a seriousness criterion, using the specific AESI form as appropriate.

The protocol defines a specific subset of AESIs and laboratory abnormalities that must be immediately reported, even if not fulfilling seriousness criteria. The following events

must be systematically reported by the treating physician as AESIs with immediate notification for all studies:

- Immune related reactions (ir-ARs) including immune-related pneumonitis, colitis, hepatitis, endocrinopathies, immune-related skin adverse reactions, nephritis, and irARs in other organs.
  - *Since Clinical manifestations of irARs are generally autoimmune-like, any AEs considered as irARs with no clear alternative etiology will need to be reported.*

**Note: for each immune related reaction the Targeted follow-up form has to be fulfilled in addition to the standard AE form.**

- Infusion related reactions (IRRs)
  - *Cases with AEs coded to infusion related reaction, hypersensitivity, type hypersensitivity, drug hypersensitivity and severe or life-threatening infusion- related reactions, including bronchospasm, anaphylaxis, anaphylactic reaction, anaphylactic shock, anaphylactoid reaction, anaphylactoid shock, angioedema, and severe hypotension, during or immediately following the initial infusion, need to be reported.*

**Note: for each infusion related reaction the Targeted follow-up form has to be fulfilled in addition to the standard AE form.**

- Pregnancy of female subject entered in a study (as well as pregnancy occurring in a female partner of a male subject entered in a study with Sanofi product);
- Pregnancy of a female exposed to a Sanofi product (as well as pregnancy occurring in a female partner of a male exposed to a Sanofi product) will be reported to the CRO *Alcedis GmbH*. It will be qualified as a SAE (only if it fulfills one of the seriousness criteria).

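### The two causality options in Section 7.3 are not exhaustive and set unequal bars, and they match neither the causality wording in 13.2 nor the reference set in the eCRF

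*Protocol*

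**What the plan says.** Section 7.3, under Evaluation of Causality, covers irAEs and SAEs and considers every treatment the patient receives, whether for CSCC or for something else. The instruction reads: "There are 2 alternative (mutually exclusive) options for this assessment. Select the one that appears most likely".

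- The related option applies when "The irAE/SAE was likely caused by one or more of patient's treatments". The suspected treatment is then to be named.
- The unrelated option describes an event that arose independently of treatment. It is met in either of two ways: "An alternative cause is suspected", or "there is no reason to suspect that one or more of the patient's treatments may have caused the irAE/SAE".

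Three other places bear on causality:

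- The parameter table in Section 9 defines the adverse event entry in the eCRF as "related/unrelated to anticancer therapy".
- Section 13.2 requires a report of any AE noticed after cessation that the physician judges "considered by him/her to be caused by Cemiplimab with a reasonable possibility".
- Section 13.3, on immune-related reactions as AESIs, says "any AEs considered as irARs with no clear alternative etiology will need to be reported".

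Sections 13 and 13.1.3 require all AEs from consent to end of study to be collected, whatever their relationship to cemiplimab.

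**The concern.** A binary causality item works only if every event falls under exactly one answer and all sites apply the same bar. In 7.3 the bars are unequal: suspicion of another cause is enough to clear a treatment, but likelihood is needed to implicate one. Between the two lies the possibly related event, which is common in a mostly older, comorbid population treated with an immunotherapy.

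Describing the safety and tolerability of cemiplimab is a stated objective (Section 6; 14.3.1.2), and relatedness is part of the recorded data. Attribution is made by physicians at about 70 sites, some university-based and some office-based. It is fixed at data entry. If possibly related events are not distinguished there, no later analysis can separate them. Section 12.2 provides quality control at 5% of sites, that is 0.05 × 70 = 3.5, or about three to four sites. It names consent, some parameters that it does not list, and completeness of SAE reporting; consistency of causality is not named.

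**Working it through.** There is no figure in the plan to reproduce, and no event counts from which to compute one. The check is to take the possible kinds of event and read each against the wording.

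| Event | Section 7.3 | eCRF (Section 9) | 13.2, if noticed after cessation |
|---|---|---|---|
| A. Cemiplimab likely the cause, no alternative suspected | Related | Related | Report |
| B. Cemiplimab possible but not likely, no alternative suspected | Meets neither definition | No threshold given | Report, if the possibility is reasonable |
| C. Cemiplimab a reasonable possibility but not likely, alternative suspected | Not related (first limb) | No threshold given | Report |
| D. A drug for a non-cancer condition likely the cause | Related | Unrelated | Not triggered |

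**Case B.** The event fails the related option because likelihood is required. It fails the second limb of the unrelated option because there is some reason to suspect a treatment, and it fails the first limb because no alternative is suspected. A physician can leave this gap by two routes. One follows "Select the one that appears most likely": a cause that is possible but less than likely loses, so the event is unrelated. The other works by elimination: the unrelated option is ruled out, so the event must be related. Both are defensible readings of the text, and they give opposite answers. Variation between sites is therefore the firm consequence here, not a shift in one direction.

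**Case C.** The first limb of the unrelated option is met as soon as an alternative is suspected, and the related option is not met. The event is recorded as not related although it satisfies the standard in 13.2. The direction is clear here: downward.

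**Case D.** This mismatch does not depend on how *likely* is read. Section 7.3 asks about all treatments, the eCRF about anticancer therapy, and 13.2 about cemiplimab. One event can take different values because the question differs.

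**Naming the treatment.** Section 7.3 asks for the suspected treatment only once the related option has been chosen. Case C events, and those case B events that are resolved as unrelated, therefore carry no attribution to cemiplimab under 7.3.

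**The case against.** The strongest reply is that these passages do different jobs. Section 7.3 classifies irAEs and SAEs, 13.2 triggers reports after cessation, and 13.3 triggers immediate notification. A trigger may be more sensitive than a classification without contradicting it. That stands: between 7.3 and 13.2 there is an unreconciled threshold, not two conflicting versions of one rule. The gap inside 7.3 and the mismatch with the eCRF do not depend on 13.2 at all.

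It can also be said that 7.3 already asks for the suspected treatment and that the eCRF entry asks for details. This helps only for events already classed as related.

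Four stronger readings are tempting, and the documents do not support them:

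- *Possibly related events are always recorded as unrelated.* Section 7.3 does not assign them expressly. Case B can go either way; only case C has a clear direction. The trigger for case C is an alternative that is suspected, not one that is merely conceivable.
- *Section 13.3 contradicts 7.3.* Under 13.3 the physician must first consider the event an immune-related reaction; the lack of a clear alternative is an added condition. The wording differs only for an alternative that is suspected but not clear, and 13.3 is a notification rule.
- *Expedited reporting to authorities is affected.* Section 13.4 refers to local and global regulations, and nothing ties it to the 7.3 label. SAEs go to the CRO on the short timeline without a causality filter.
- *The related share is understated by a given number of percentage points.* The documents give neither event counts nor the share of possibly related events, so any such figure would only return the share assumed.

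Finally, the protocol defines no treatment-related event rate as an endpoint. The consequence lies in descriptive safety data.

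**Conclusion.** The point holds as a defect in a stated classification rule. Followed as written, 7.3 leaves possibly related events without an answer when no alternative is suspected. It records them as not related when one is. Its threshold differs from that in 13.2, and its reference set differs from those of the eCRF and 13.2.

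The harm is inconsistent relatedness classification, with some downward bias in the subset with a suspected alternative cause. Capture of adverse events is not affected. The size is unknown and cannot be derived from the documents; it depends on how many events are possibly related and on how each site closes the gap. The conclusion rests on the protocol wording alone and assumes that sites apply 7.3 as written when they fill in the relatedness field. The change should be made, because the information cannot be recovered after entry, but it does not threaten the primary analysis of TTNT.

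**What to change.** Reconcile 7.3, the eCRF and 13.2 to one causality threshold with two exhaustive options. One choice is a reasonable possibility that the treatment caused the event against no reasonable possibility; this uses the standard already in 13.2. Remove the instruction to choose whichever option appears more likely, since it brings back a different bar.

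Align the reference set, and record relatedness to cemiplimab as its own eCRF item, separate from relatedness to other treatments, both anticancer and non-cancer.

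The cost is a rewording of 7.3, one eCRF item, and causality queries on events already entered. The reported related rate may come out somewhat higher. No treatment or clinical management changes.

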## 8 SELECTION OF PATIENTS

This section outlines definitions of the specific patient population evaluated in this observational study and the patient selection criteria.

### 8.1 SAMPLE SIZE

Considering the fact that this is a descriptive study, there must be no testing of an *a priori* hypothesis. In our study the primary objective is to describe TTNT or death in 200 patients with advCSCC initially treated with Cemiplimab (prospective cohort) or 200 patients with other therapeutic approaches (retrospective cohort). Sample size justification is described in detail in our synopsis section "STATISTICAL METHODOLOGY."

Approximately 60 participating expert centers located in Germany, and 5 centers from each Austria and Switzerland respectively will participate in the study. Participating centers will include different professional groups with permission for systemic treatment either in university clinics or an office-based setting to get a representative picture of the real-world advCSCC treatment.

#### Definition of the patient cohorts

For this observational study, data will be collected for two cohorts, a prospective cohort and a retrospective cohort. In both cohorts, data of advCSCC patients with mCSCC or ladvCSCC will be collected.

The mCSCC cohort is defined as those with locoregional nodal as well as distant metastasis.

The lacSCC cohort is defined as patients that could not be treated with a curative intent either by surgery, radiotherapy or both based on a decision of an interdisciplinary tumor board.

### 8.2 INCLUSION CRITERIA

Prospective cohort:

- Planned treatment for advCSCC adult patients  $\geq 18$  yrs who are at the first time initiated on Cemiplimab treatment according to SmPC of Cemiplimab
- Able to understand and complete study-related questionnaires
- Signed ICF

Retrospective cohort:

- Patients  $\geq$  18 years with advCSCC first diagnosed between Jan/2012 and Aug/2019
- From these patients only anonymous data will be collected. Thus no Sanofi-ICF is needed. This procedure allows including data from patients who are no longer alive (planned).

### **8.3 EXCLUSION CRITERIA**

Prospective cohort:

- Missing ICF
- advCSCC of unknown primary origin
- Any condition that, in the opinion of the investigator, may interfere with patient's ability to participate in the study, such as severe cognitive impairment or other comorbidities that would, in the opinion of the investigator, predictably limit compliance with the intended treatment plan, or prevent the patient from adequately completing QOL assessments.

Retrospective cohort:

- Patients enrolled in clinical trials for advCSCC treatment
- advCSCC of unknown primary origin

#### **Premature withdrawal from the study**

A patient has the right to withdraw from the study at any time, for any reason, and without any penalties resulting from this decision.

The participating physician should make every effort to re-contact the patient to determine his/her health status, including at least his/her vital status. In case of Cemiplimab treatment discontinuation at any time, the documentation will continue until month 36 or patient's death to assess outcome and further therapeutic modalities.

For the retrospective cohort: no Sanofi-ICF will be collected.

#### **Study completion**

Prospective cohort: Each patient will be considered to have completed this study at the time they complete 3 years of follow up at the time they withdraw consent for further participation, or at the time of death.

Patients will remain in the study even if they discontinue cemiplimab permanently or temporarily.

Patients who discontinue treatment and/or choose not to continue with follow up visits and questionnaires will still be followed for survival at 3 month intervals, provided they do not withdraw their consent completely for the full 3 years duration of follow-up.

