	Immunosuppressive therapy		
	Substantial tumor syndromes		
	Specification of substantial tumor syndromes		
	Disease & medication		
Primary diagnosis	Date of diagnosis		All primary diagnosis at Baseline
	Evaluation		
	Tumor status		
	Histological subtype		
	Tumor localization		
	TNM classification		
	Clinical stage		
	ECOG performance status	Defined as 0, 1, 2, 3, 4, measured at advanced diagnosis, at each LOT, prior to and following radiation for early disease, where applicable	
	Infiltration depth and bone involvement		
	Initial treatment of primary tumor		
	Primary surgery	If yes: date, procedure	
	Re-excision	If yes: date, procedure, micrographic controlled surgery, final resection border, cumulative safety distance (cm)	
	Tumor size of the histo block	horizontal tumor diameter (cm), vertical tumor size (mm), differentiation level	
	High risk factors		
	Further synchronous CSCC		
	Curative surgery of advCSCC	Yes or no	
	Tumor board	Yes or no. If yes: decision realized (yes or no)	
	Metastases	Locoal regional or distant	
Recurrence	Date of diagnosis		All recurrence

diagnosis			diagnosis at Baseline
	Evaluation		
	Tumor status		
	Histological subtype		
	Tumor localization		
	TNM classification		
	Clinical stage		
	ECOG performance status	Defined as 0, 1, 2, 3, 4, measured at advanced diagnosis, at each LOT, prior to and following radiation for early disease, where applicable	
	Infiltration depth and bone involvement by local recurrence		
	Initial treatment of primary tumor		
	Primary surgery	If yes: date, procedure	
	Re-excision	If yes: date, procedure, micrographic controlled surgery, final resection border, cumulative safety distance (cm)	
	Tumor size of the histo block	horizontal tumor diameter (cm), vertical tumor size (mm), differentiation level only by local recurrence	
	High risk factors by local recurrence		
	Further synchronous CSCC by local recurrence		
	Curative surgery of ladvCSCC	Yes or no	
	Tumor board	Yes or no. If yes: decision realized (yes or no)	
	Metastases	Locoal regional or distant	
Restaging	Date of diagnosis		All restaging parameters at Baseline
	Evaluation		
	Tumor status		
	Histological subtype		
	Tumor localization		

	TNM classification		
	Clinical stage		
	ECOG performance status	Defined as 0, 1, 2, 3, 4, measured at advanced diagnosis, at each LOT, prior to and following radiation for early disease, where applicable	
	Infiltration depth and bone involvement		
	Differentiation level		

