	High risk factors		
	Further synchronous CSCC		
	Response	Yes or no	
	Tumor board	Yes or no. If yes: decision realized (yes or no)	
	Metastases	Locoal regional (type, single or multiple) or distant (localization, single or multiple)	
Surgery	Date of surgery		All at Baseline
	Evaluation		
	Marked lymph nodes (sentinel)	Yes or no	
	Surgery procedure		
	Diameter of largest lymph node	(cm)	
	Capsule break	Yes or no	
	Number of removed lymph nodes		
	Number of lymph nodes with metastases	Maximal size (cm)	
	Completing lymph node dissection	Yes or no If yes: date, procedure, number of dissected lymph nodes, number of lymph nodes with metastases,	
	Residual status		
	Global status of the patient	Tumor free (yes or no)	
Systemic therapy	Intention		All at Baseline
	Line	(1st-line, 2nd-line, ...)	

	Regimen		
	Type	(table with medicinal products, table with study medicinal products, table with toxicity)	
	Therapy	From (date) to (date) or ongoing, number of cycles, application,	
	Best response		
	Reason for therapy completion		
	Table with medicinal products	From (date) to (date) or ongoing. Active ingredient / brand name	
	Table with study medicinal products	From (date) to (date) or ongoing. Type, study, study trial	
	Table with toxicity	Date, event term, severity, medical procedure, outcome.	
Locoregional therapy	Date	From (date) to (date)	All locoregional therapy at Baseline
	Medical examination		
	Intention		
	Therapy procedure		
	Residual status	Locoregional efficacy	
	Global status of the patient	Tumor free or do metastases exist at other location?	
Radio Therapy	Date	From (date) to (date)	All radio therapy at Baseline
	Medical examination		
	Intention		
	Organ system		
	Laterality		
	Type		
	Dosage	(Gray)	
	Residual status	Response rate (no, partial, complete)	
	Global status of the patient	do metastases exist at other location?	
Final patient treatment	Date of last visit		Last and final visit at end of follow-up after 36 months

	Reason of last visit		
	Tumor death relation		
	Date of death		

The following table demonstrate a time table for the e-CRF parameter

	Baseline	Start of Treatment	Visits: Month after start of treatment						
			3	6	9	12	18	24	36
Informed consent	x								
Patient characteristics: Gender, age, skin type etc.	x								
Medical History									
- General medical history (comorbidities, etc.)	x		x	x	x	x	x	x	x

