- Any prior autoimmune diseases	x								
- Tumor related history (primary diagnosis, relapses, treatments, etc.)	x		x	x	x	x	x	x	x
Current TNM, Grading (at baseline) and R- Situation if indicated	x		x	x	x	x	x	x	x
QoL (EORTC- QoL Core	x		x	x	x	x	x	x	x

30)									
Adverse Events			x	x	x	x	x	x	x

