##### **14.3.1.2 Secondary variables of the prospective cohort**

- \* DOR , DCR (CR+PR+SD) at 3, 6, 9, 12, 18, 24, 36 months
- \* Patient experience, functional status, QoL and pain, in a real-world setting for patients with advCSCC at 3, 6, 9, 12, 18, 24 and 36 months
- \* Safety data on study participants defined on paragraph 13
- \* Characteristics of patients who receive Cemiplimab as treatment for advCSCC in a real-world setting
- \* OS defined as duration from current mCSCC or ladvCSCC diagnosis and also from the initiation of each LOT until death or end of follow up
- \* Proportion of patients surviving at month 3, 6, 9, 12, 18, 24 and up to months 36 from initiation of systemic therapy

- \* PFS defined as time from first documented systemic cemiplimab therapy initiation until progression or treatment discontinuation due death or end of follow up
- \* Patient demographics and baseline characteristics (incl. age, performance status etc.) at study entry
- \* Characterization of Cemiplimab usage patterns
- \* Cemiplimab treatment regimen (initial dose and date of initiation and regimen changes)
- \* Treatment prior to and post Cemiplimab treatment, incl. surgery, radiation, systemic therapies incl. agents administered, dose, frequency and duration
- \* Surgery post initiation of Cemiplimab treatment
- \* DOT
- \* TNM stage (AJCC or UICC)
- \* Observed rates, reasons and timing of the discontinuation of Cemiplimab
- \* TTF including lack of response and discontinuation due to AE
- \* Change in patient reported QoL as per EORTC-QLQ-C30 QoL questionnaire during treatment with Cemiplimab (for prospective cohort only)

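### Prospective cohort: the follow-up and CRF rules conflict on recording next systemic therapy and response after baseline, and patients who decline visits may have unrecorded primary events

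*Protocol*

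**What the plan says.** **Follow-up.** Under Study completion in section 8.3, patients who stop treatment and/or "choose not to continue with follow up visits and questionnaires will still be followed for survival at 3 month intervals", as long as consent is not fully withdrawn. The paragraph just before it in the same section (Premature withdrawal) says that when cemiplimab is stopped "the documentation will continue until month 36 or patient's death to assess outcome and further therapeutic modalities". The Synopsis (Main data collected) and section 7.1 give the same rule. Premature withdrawal also asks the physician to re-contact the patient about health status, with vital status as the minimum.

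**Primary event.** The CRF definitions give TTNT as "Defined as time from start of Cemiplimab treatment to the start of next systemic therapy or death". Section 14.3.1.1 agrees and leaves out best supportive care.

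**CRF parameter table (section 9).** The restaging block, which holds the response item, is marked "All restaging parameters at Baseline". The surgery and systemic therapy blocks (the latter with line, dates and best response) are each marked "All at Baseline". Locoregional therapy and radiotherapy are likewise placed at baseline.

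**CRF time table (section 9).** The row "Tumor related history (primary diagnosis, relapses, treatments, etc" is ticked at baseline and at all seven later visits.

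**Endpoints.** Section 14.3.1.2 asks for "DCR (CR+PR+SD) at 3, 6, 9, 12, 18, 24, 36 months", together with DOR and treatment after cemiplimab. Section 14.3.2.2 asks for ORR with a confidence interval.

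**The concern.** TTNT needs two facts per patient: whether and when a new systemic therapy began, and whether and when the patient died. A contact that asks only about survival supplies the second. Patients who have stopped cemiplimab or stopped attending are plausibly those close to a next line of therapy, so a gap there would fall on the primary event itself. A patient whose new therapy is not seen counts as event-free until death or last contact. The error goes one way and makes TTNT on cemiplimab look longer.

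The parameter table raises a second question. Read alone, it gives no post-baseline entry for the later therapy lines that TTNT needs, or for the response categories that DCR, ORR and DOR need.

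**Working it through.** **1. Which patients does each rule cover?**

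| Patient | Rules that apply | Next therapy recorded? |
|---|---|---|
| Stops cemiplimab, keeps visits | Synopsis, 7.1 and 8.3 Premature withdrawal: documentation to month 36 or death, "to assess outcome and further therapeutic modalities". 8.3 Study completion: survival every 3 months | Yes under the first group; not stated under the second. The texts conflict |
| Declines visits, keeps consent | 8.3 Study completion: survival every 3 months. 8.3 Premature withdrawal: re-contact, at least vital status | Not explicitly required by either |
| Withdraws consent fully | None | Not applicable |

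The conflict comes from the and/or in Study completion, which joins the first two rows. The gap is in the second row.

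**2. Which CRF entries exist after baseline?**

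| Item | Parameter table | Elsewhere |
|---|---|---|
| Systemic therapy, surgery, radiotherapy, locoregional therapy | Baseline | Treatments row of the time table at months 3-36; medication and cemiplimab survey at all examinations (7.3); concomitant treatment throughout (10); eCRF period to latest follow-up or death (9) |
| Progression and its date | Months 3-36 | - |
| Restaging, including response | Baseline | RECIST 1.1 evaluation (7.3) and best response (11.2.1), without a visit schedule |
| CR/PR/SD at a given visit | No post-baseline entry | No row in the time table |

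QoL, comorbidities and adverse events in the same parameter table carry baseline plus months 3-36, so the baseline-only label was entered block by block.

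**3. The plan's own precision, as a yardstick.** The Synopsis gives 200 patients, 180 events and, for a median of 30 months, limits 26.1 to 34.9 (width 8.9). The exponential chi-square interval with d = 180 is 30 × 360/χ²(0.975; 360) = 26.06 to 30 × 360/χ²(0.025; 360) = 34.91. The width is 8.86 and the half-width 4.43 months. The stated figure reproduces and is not in dispute.

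**4. Effect of missed therapy starts.** Assumptions, none of them from the documents except the 30-month median, which is one of the Synopsis scenarios:
- exponential times with total TTNT hazard λ = ln 2/30;
- a share r of that hazard is therapy starts, the rest deaths;
- a fraction u of therapy starts is not seen, and those patients are followed for death only, at hazard (1 − r)λ.

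The apparent event-free curve is S(t) = (1 − u)·exp(−λt) + u·exp(−(1 − r)λt). With x = exp(−λt), the apparent median solves (1 − u)x + u·x^(1 − r) = 0.5, and t = 30 × (−ln x)/ln 2.

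- r = 0.6, u = 0.10: 0.9x + 0.1x^0.4 = 0.5 gives x = 0.4732 and t = 32.4 months (+8%).
- r = 0.6, u = 0.20: 0.8x + 0.2x^0.4 = 0.5 gives x = 0.4443 and t = 35.1 months (+17%).

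The same u range with other shares:

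| r | u = 0.10 | u = 0.20 |
|---|---|---|
| 0.4 | 31.4 (+5%) | 33.0 (+10%) |
| 0.6 | 32.4 (+8%) | 35.1 (+17%) |
| 0.8 | 33.6 (+12%) | 38.0 (+27%) |

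At r = 0.6 the shift is 2.4 to 5.1 months, against a planned half-width of 4.43 months. If patients were instead censored at the missed start, the factor would be 1/(1 − 0.6u), that is 1.064 to 1.136. Follow-up to death is the closer match to Study completion, because survival contact continues.

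**The case against.** Two stronger readings are tempting, and the documents support neither.

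A reader might infer that everyone who stops cemiplimab is followed for survival only. Study completion does not contain the word only, and its preceding sentence keeps these patients in the study. The Synopsis, section 7.1 and Premature withdrawal all continue documentation of later therapies, and sections 7.1 (consent paragraph) and 10 keep the patients eligible. For this group the fault is loose wording that conflicts with three clearer statements.

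A reader might also infer that later therapy and response are not collected at all. The time table names treatments at every visit, sections 7.3, 9 and 10 provide for treatment data over time, and progression is listed at months 3-36. Since DCR is CR+PR+SD, in an evaluated patient it is the complement of progression. The section 2.2 flow chart did not survive in the text available and may schedule more.

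This narrows the point but does not remove it. None of those places explicitly requires a next-therapy date for a patient who no longer attends. The treatments row contradicts the parameter table rather than settling which applies. Progression entries do not separate CR and PR from SD, as ORR and DOR require, and do not distinguish disease control from no evaluation. The missed-event rates are assumptions, and the number of patients who decline visits is not stated.

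Single entry in the retrospective cohort is by design and is no defect.

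**Conclusion.** The point holds for the prospective cohort as an internal contradiction plus one gap. The contradiction is twofold: Study completion against the Synopsis, section 7.1 and Premature withdrawal; and the CRF parameter table against the time table, sections 7.3 and 10, and the response and later-therapy endpoints. The gap is that recording a next systemic therapy is not explicitly required for patients who decline visits but keep consent.

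The direction of bias is upward for median TTNT. Its size cannot be derived from the documents. The 8-17% range rests on an exponential model, a 60% share of therapy starts among events, and 10-20% of all therapy starts missed with follow-up for death only. If few patients decline visits, the effect will be smaller. For response, no visible CRF row schedules CR/PR/SD after baseline, a statement limited by the missing flow chart.

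**What to change.** 1. **Section 8.3, Study completion.** Reconcile it with the Synopsis, section 7.1 and Premature withdrawal, so that reduced follow-up applies only to patients who decline visits and stopping cemiplimab alone leaves full documentation in place.
2. **3-month contacts.** At each one, or from medical records within the consent given, record vital status and the start date and type of any new systemic therapy.
3. **CRF parameter table.** For the prospective cohort, change the visit entry for systemic therapy, surgery, radiotherapy, locoregional therapy and restaging/response to baseline plus months 3, 6, 9, 12, 18, 24 and 36. Add matching time table rows, including one for response category, and check them against the section 2.2 flow chart.

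The cost is one extra question at contacts already planned, a corrected CRF column and a small amount of site data entry. Treatment and visit frequency do not change.
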